4. STUDY DESIGN

4.1. Overview

This is a Phase 2, open label study of ARD-101 in subjects with unsatisfactory weight management at least one year after bariatric surgery (sleeve gastrectomy or gastric bypass).

This study has a planned enrollment of 30 subjects (approximately 15 for each preceding surgical procedure) and will be conducted in a single center in the United States.

The study will consist of a Screening Period (up to 28 days), a Run-in Visit Period (up to 14 days), a Treatment Period (28 days), and a Follow-up Period (EOS Visit within 14 days after receiving the last dose of ARD-101). The screening procedures will be initiated upon completion of the informed consent process. Following completion of screening procedures and confirmation of eligibility, subjects will be enrolled to receive ARD-101.

ARD-101 will be administered orally under fasting conditions (approximately 60 minutes **before** breakfast and approximately 60 minutes **before** dinner) at 200 mg BID for 28 days. Subjects will receive treatment in an outpatient setting and will be instructed to visit the clinical center periodically as scheduled in Table 1 for safety and efficacy assessments. The treatment may be discontinued due to intolerable toxicity, withdrawal of informed consent, discretion of principal investigator or end of the study.

All available safety and tolerability data will be evaluated throughout study conduct. Pharmacodynamic data will be analyzed after study completion.

4.2. Justification for Dose

The dose of 200 mg BID was chosen based on the available nonclinical studies and clinical data. As described above, this dose has been found safe in the first-in-human trial and the pharmacokinetics support the prescribed dose level and duration.

4.3. Study Duration

The duration of participation for each subject will be up to approximately 84 days (12 weeks).

- Screening Period: Up to 28 days (4 weeks)
- Run-in Visit: Up to 14 days (2 weeks)
- Treatment Period: 28 days on ARD-101

- Follow-up Period: 14 days (2 weeks). The EOS Visit will occur within 14 days after receiving the dose of ARD-101

4.4. Study Completion

For the entire study, study completion is defined as the last visit of the last subject for any protocol related activity (last subject, last visit). For individual subjects, study completion is defined as the time of the subject's last data collection.

4.5. Early Termination

If a subject withdraws prematurely after dosing, all data normally collected should be collected at the time of premature discontinuation. If deemed necessary by the Principal Investigator, the subject will be asked to return at the regularly scheduled EOS Visit.

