	
 ▪ Circulating levels of bile acids, ferritin, leptin, and adiponectin at run-in visit and end of treatment (day 28) performed during the MMTT • Body composition as measured by bioelectrical impedance scale • Body composition and hepatic steatosis by magnetic resonance imaging-derived proton density fat fraction (MRI-PDFF) + full body composition scan pretreatment and end of treatment • The change in homeostatic model assessment for insulin resistance (HOMA-IR) at the end of treatment from the baseline • The change in fasting blood glucose at the end of treatment from the baseline • Hunger and control of eating as measured by Likert and visual analogue scales, respectively • Change in indirect calorimetry • The fecal samples will be collected during the run-in visit and on day 28 for microbiome analysis to evaluate potential effects of the study medication on fecal microbiome profile (optional for subjects) • Phenotypic bitter taste test (using commercially available test strips/kis) during the run-in visit of the study (optional for subjects)
Study Design	
This is a Phase 2, open label study of ARD-101 in subjects with relevant weight regain at least one year after bariatric surgery comparing inpatient metabolic dynamics.
 
A total of approximately 30 subjects (15 post sleeve gastrectomy and 15 post gastric bypass surgery) will be enrolled in the clinical study.
 
A screening process will be initiated upon completion of the informed consent process. Subjects will be assessed for eligibility through screening tests conducted within 28 days prior to enrollment. Following completion of screening tests and confirmation of eligibility, subjects will be enrolled to receive ARD-101.
 
All available safety and tolerability data will be evaluated throughout study conduct. Pharmacodynamic data will be analyzed after study completion.
 
Subjects will be receiving treatment in an outpatient setting and will be instructed to visit the clinical center periodically as scheduled in Table 1 for safety and efficacy assessments. The treatment may be discontinued due to intolerable toxicity, withdrawal of informed consent, discretion of principal investigator or end of the study.
 
All subjects will be followed up for approximately 14 days after the last dose of study drug.

Test Product, Dose, and Mode of Administration	ARD-101 at 200 mg BID administered orally for 28 days

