	
2 years prior to enrollment (Note: one unit = 12 ounces of beer, 4 ounces of wine or 1 ounce of spirits)
 
 16. Smoking any amount within 3 months prior to enrollment 17. Excessive consumption of tea, coffee, and/or caffeinated beverages (more than 8 cups, 250 mL for each cup) every day within 3 months prior to enrollment 18. Symptomatic viral, bacterial (including upper respiratory infection), or fungal (non-cutaneous) infection within 1 week prior to enrollment 19. History of human immunodeficiency virus antibody, hepatitis C antibody or hepatitis B virus surface antigen 20. A history of psychiatric and psychological condition that, in the judgment of the investigator, may interfere with the planned treatment and follow-up, affect subject compliance or place the subject at high risk from treatment-related complications 21. Poor venous access or inability to tolerate venipuncture 22. Any condition or active drug treatment that the investigator or primary physician believes may not be appropriate for participating in the study
Duration of Study	
The duration of participation for each subject will be approximately 84 days (12 weeks)
 
 • Screening Period: Up to 28 days (4 weeks) • Run-in Visit: Up to 14 days (2 weeks) • Treatment Period: 28 days on ARD-101 (4 weeks) • Follow-up Period: 14 days (2 weeks). The End of Study (EOS) Visit will occur within 14 days after receiving the dose of ARD-101
Pharmacodynamic Evaluation	
All subjects will be required to provide blood samples at defined time points and at the end of treatment visit. These blood samples will be used to explore the parameters described in the endpoint setting. The Control of Eating Questionnaire (CoEQ) will be administered at the timepoints indicated in Table 1.

Safety Evaluations	
Adverse events (AE) will be collected from the time of informed consent until 14 days after the last administration of study drug. Safety laboratory assessments, including CBC, chemistries, coagulation tests, urinalysis, and thyroid function, along with ECGs, , and vital signs will be obtained. All concomitant medications will be recorded. All adverse events will be followed to resolution or stabilization. Only TEAE will be summarized.

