6.5. Dose Modification

The dose level may not be reduced. If any \geq Grade 3 toxicities or any intolerable Grade 2 toxicity occurs, treatment should be discontinued permanently. Intolerable toxicity is defined as, in the opinion of Principal Investigator and Medical Monitor, any toxicity that poses a significant health risk to the subject. Treatment may continue on any Grade 1 toxic reactions or Grade 2 anorexia or Grade 2 weight loss. For any other Grade 2 toxicities, dosing may be interrupted for up to 3 days and may be resumed at the medical judgment of Investigator once the toxicity has resolved to Grade 0-1. A missed dose should not be made up. In the event of multiple toxicities, dosing management should be based on the worst toxicity observed. Subjects will be instructed to notify Investigators at the first occurrence of any adverse symptom.

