8.2. Safety Variables

8.2.1. Adverse Events

Adverse event reporting will begin for each subject from the date the ICF is signed and will continue until the EOS Visit.

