8.2.1.2. Recording of Adverse Events

Adverse events should be collected and recorded for each subject from the date the ICF is signed until the end of their participation in the study, i.e., the subject has discontinued or completed the study.

Adverse events may be volunteered spontaneously by the subject, or discovered by study staff during physical examinations or by asking an open, non-leading question such as ‘How have you been feeling since you were last asked?’ All AEs and any required remedial action will be recorded. The nature of AE, date (and time, if known) of AE onset, date (and time, if known) of AE outcome to date, severity and action taken of the AE will be documented together with the Principal Investigator’s assessment of the seriousness of the AE and causal relationship to study drug and/or study procedure.

All AEs should be recorded individually in the subject’s own words (verbatim) unless, in the opinion of the Principal Investigator, the AEs constitute components of a recognized condition, disease or syndrome. In the latter case, the condition, disease or syndrome should be named rather than each individual symptom. The AEs will subsequently be coded using the Medical Dictionary for Regulatory Activities (MedDRA). Severity of AEs will be graded using the Toxicity Grading Scale for Healthy Adult and Adolescent Volunteers Enrolled in Preventive Vaccine Clinical Trials (September, 2007).

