8.2.1.4. Reporting of Serious Adverse Events

The Principal Investigator will review each SAE and evaluate the intensity and the causal relationship of the event to study drug. All SAEs will be recorded from signing of the ICF until the EOS Visit. Serious AEs occurring after the EOS Visit and coming to the attention of the Principal Investigator must be reported only if there is (in the opinion of the Principal Investigator) reasonable causal relationship with the study drug.

The Principal Investigator is responsible for providing notification to Sponsor of any SAE, whether deemed study medication-related or not, that a subject experiences during their participation in study within 24 h of becoming aware of the event.

Initial reports of SAEs must be followed later with detailed descriptions, including clear photocopies of other documents as necessary (e.g., hospital reports, consultant reports, autopsy reports), with the subject's personal identifiers removed.

Information on SUSARs will be collected and reported to the regulatory authority and the IEC as required per guidelines.

If the SUSAR is fatal or life-threatening, associated with the use of the study medication, and unexpected, the regulatory authority and the IEC will be notified per guidelines after being made aware of the case. Additional follow-up (cause of death, autopsy report, hospital report) information should be reported per guidelines. SUSARs which are not fatal and not life-threatening are to be reported per guidelines.

The Sponsor will notify the Investigators of relevant information about SUSARs that could adversely affect the safety of subjects in a timely fashion. Follow-up information may be submitted if necessary. The Sponsor will also provide annual safety reports for submission to the regulatory authority and the IEC responsible for the clinical study. These updates will include information on SUSARs and other relevant safety findings.

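### Subjects who withdraw early after dosing have no required check for new adverse events in the 14 days after the last dose, although the synopsis promises collection over that period

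*Combined protocol and SAP*

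**What the plan says.** The synopsis makes two commitments, neither with an exception for early withdrawal. The Study Design row says "All subjects will be followed up for approximately 14 days after the last dose of study drug". The Safety Evaluations row says "Adverse events (AE) will be collected from the time of informed consent until 14 days after the last administration of study drug".

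The operative sections differ for a subject who withdraws prematurely after dosing:

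- Section 4.5 asks for data at the time of leaving, and then: "If deemed necessary by the Principal Investigator, the subject will be asked to return at the regularly scheduled EOS Visit".
- Section 8.2.1.2 records AEs "until the end of their participation in the study, i.e., the subject has discontinued or completed the study".
- Section 8.2.1 says AE reporting "will continue until the EOS Visit", and section 8.2.1.4 says "All SAEs will be recorded from signing of the ICF until the EOS Visit". An early withdrawer may never have that visit.
- Section 4.1 places the visit itself as "EOS Visit within 14 days after receiving the last dose of ARD-101", so 14 days is its upper limit, not its target.

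The incidence of TEAEs is a secondary endpoint (section 3.2). Section 9.7.1 ends each subject's TEAE period at the last occasion on which AEs were assessed.

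**The concern.** A site that follows sections 4.5 and 8.2.1.2 to the letter can close AE recording on the day a subject leaves. The synopsis would have it stay open for another 14 days. Because section 9.7.1 ties the TEAE period to the last assessment, the shorter look passes into the TEAE tables without any flag. Section 7.1 allows withdrawn subjects to be replaced, so those tables would combine subjects who had a scheduled post-treatment AE review with subjects who did not.

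Two things are at stake. One is ascertainment of new or delayed events in subjects who left early, some of them because of an AE. The other is consistency between what the synopsis commits to and what the site is told to do. The human repeat-dose data summarised in section 2.4.1.2 cover 14 days of dosing in healthy volunteers with BMI 18 to 30. This trial doses for 28 days in a post-bariatric population with BMI 35 to 60.

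**Working it through.** The plan states no figure to reproduce. The check is to follow each type of subject through the text.

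**Completer.** Last dose on day 28; EOS up to 14 days later, so by about day 28 + 14 = 42. Table 1 marks AE monitoring at that visit. The full 14 days are not assured, because the visit may fall sooner, but a post-treatment AE review is scheduled.

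**Subject who stops drug but stays in the study.** Sections 6.6, 6.9.1 and 6.9.2 speak of stopping study drug, not of leaving the study. The synopsis says that treatment may be discontinued and then promises follow-up to all. The natural reading is that this subject keeps the EOS visit, though no sentence says so.

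**Subject who leaves the study and is not recalled.** Section 4.5 collects data on leaving; section 8.2.1.2 then ends recording. If the last dose and the departure both fall on day d (an assumption), the synopsis window runs to day d + 14, and the required active window ends on day d. The share not actively covered is 14/(d + 14):

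- d = 7: 14/21 = 67%
- d = 14: 14/28 = 50%
- d = 21: 14/35 = 40%

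These are shares of one subject's own window for assumed days. They are not effects on the endpoint.

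**Subject who leaves and is recalled.** Section 4.5 refers to the visit as regularly scheduled. If that means about day 42, a subject whose last dose was on day 7 returns 42 − 7 = 35 days after it. The discretionary recall therefore does not reliably deliver a 14-day check either.

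**How many.** The documents give no expected withdrawal rate. In the multiple-dose part of the first-in-human study, 1 of 13 ARD-101 subjects discontinued (7.7%, exact 95% CI 0.2% to 36%). Section 2.4.3 describes that event as Grade 1, which section 6.5 here lets continue, so the figure does not predict the rate in this trial. Of the five withdrawal reasons in section 7.1, a required contact could reach three: adverse event, protocol violation and other.

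**What it does to the endpoint.** A subject adds to missed any-TEAE incidence only if there was no TEAE before leaving, a first TEAE occurred afterwards, and nobody reported it. A subject who leaves because of an on-treatment AE fails the first condition and is already counted. TEAEs on drug were common in the multiple-dose part: (1 + 3 + 3)/(4 + 5 + 4) = 7/13 = 54% (Table 6). Tables by preferred term and severity could still miss a new event in someone already counted once.

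**Safety tests on leaving.** Section 4.5 does not say which visit's assessments apply at early termination. As Table 1 reads, haematology and the pregnancy test after Day 1 appear only at EOS, so a subject who leaves early could miss both.

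**The case against.** The case for leaving the text alone has real substance.

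- **Safeguards exist.** Section 6.5 says "Subjects will be instructed to notify Investigators at the first occurrence of any adverse symptom", and section 8.2.1.2 accepts volunteered AEs. Section 8.2.1.5 follows events already experienced. Section 8.2.1.4 still requires reporting of causally related SAEs that come to the investigator's notice after EOS. Section 7.1 requires an effort to learn why a subject left, and section 8.2.1.6 follows pregnancies after withdrawal. All of this stands, so it would be wrong to say that events after withdrawal are simply lost. What none of these provisions requires is that someone ask about new events in the 14 days after the last dose.
- **Stopping drug is not leaving the study.** A reader might infer that every subject taken off drug for toxicity drops out of AE collection. The text does not support that, and the point is confined to subjects who leave. That group is not empty: section 7.1 lists an adverse event as a reason for ending participation, and the protocol never clearly separates the two states.
- **The exposed period is short.** The longest geometric mean half-life in Table 4 is 18.4 h (imprecise for three subjects), and five half-lives are 92 h, just under 4 days. Section 2.4.3 describes GI symptoms as early and self-limiting. This lowers the likely yield of a check at 14 days. It does not remove the synopsis commitment, and 3 of 6 subjects still had quantifiable drug 72 hours after a single 240 mg dose.
- **Nothing is compared.** The trial is single-arm with descriptive summaries, so no between-group contrast is biased. That is correct, and it limits the consequence.

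**Conclusion.** The inconsistency is real, and no other section resolves it. For subjects who withdraw from the study early after dosing, the operative text can give a shorter active AE window than the synopsis promises and than completers receive. It is a small point that is cheap to correct: the number of such subjects is unknown and probably small, the likely effect on any-TEAE incidence is minor, and the primary weight endpoint is not touched.

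Two further inferences should be resisted. First, the EOS visit is not discretionary for everyone: the discretion sits in section 4.5 alone and applies only after premature withdrawal. Second, no percentage-point understatement of TEAE incidence can be quoted. It would need a withdrawal count that the documents do not give, and would have to assume that none of those subjects already had a TEAE.

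The conclusion assumes that discontinued in section 8.2.1.2 means having left the study. If a site read it as having stopped drug, more subjects would be affected.

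**What to change.** - **Section 4.5:** require an EOS visit, or at least a telephone safety contact, about 14 days after the actual last dose for every dosed subject who has not withdrawn consent. State that subjects who only stop study drug remain in follow-up.
- **Sections 8.2.1, 8.2.1.2 and 8.2.1.4:** run AE and SAE collection until 14 days after the last dose, so that both share one window with the synopsis.
- **Sections 4.1 and 4.3 and the synopsis duration row:** change the EOS timing to about 14 days after the last dose, so that the visit and the collection window agree for completers as well.
- **Section 4.5:** state that the early-termination visit includes the EOS safety tests (haematology, chemistry, urinalysis and, where applicable, the pregnancy test).

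The cost is a wording amendment across these sections and one visit or call each for what are likely to be a few subjects, which the synopsis already promises. Some may decline, and subjects who are lost or withdraw consent will stay out of reach.

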5. STUDY POPULATION

The study population will consist of male and female subjects at least one year after sleeve gastrectomy or gastric bypass surgery). Subjects must be able to provide written informed consent and meet all the inclusion criteria and none of the exclusion criteria.

5.1. Number of Subjects

A total of approximately 30 subjects will be enrolled in the clinical study.

If any assessments for inclusion or exclusion criteria are out of permissible ranges during the Screening Period, repeat assessments may be allowed for those subjects at Principal Investigator's discretion.

5.2. Inclusion Criteria

Subjects must meet all the following criteria to be eligible for participation in this study:

1. Male and female subjects, 18-75 years of age
2. Willing and able to provide signed and dated informed consent prior to any study-related procedures and willing and able to comply with all study procedures
3. Body Mass Index (BMI) of $\geq 35 - 60$ kg/m² during the Screening Period
4. Status of at least 1-year post sleeve gastrectomy or gastric bypass surgery
5. One of the following:
 - Weight loss of at least 50% of their excess weight at their nadir, and weight regain at least 20% of their nadir weight loss. Excess weight is defined as maximum preoperative weight – weight corresponding to BMI 25 kg/m²
 - Excess weight loss less than 50% at the subject's nadir weight
6. Subjects with rescue surgery (e.g. gastric band to sleeve gastrectomy or gastric bypass; sleeve gastrectomy to gastric bypass) will be allowed, with time since second surgery of at least 12 months
7. Subjects with a history of revision procedures will be allowed if at least 6 months have passed since the procedure and weight has not deviated more than 5% in the 3 months prior to enrollment
8. No abnormal findings or abnormalities of clinical significance in vital signs, physical examination, clinical laboratory tests (CBC, urinalysis, blood biochemistry, coagulation,

pregnancy test (females), urine drug test, nicotine test, etc.), 12-lead electrocardiogram (ECG) during the Screening Period

9. Serum creatinine, alkaline phosphatase, hepatic enzymes (aspartate aminotransferase, alanine aminotransferase) and total bilirubin (unless the subject has documented Gilbert syndrome) not exceeding 1.5-fold the upper laboratory norm and eGFR >30 mL/min
10. Standard 12-lead ECG parameters after 10 minutes resting in supine position in the following ranges; 120 ms < PR < 220 ms, QRS < 120 ms, QTc ≤ 430 ms if male, ≤ 450 ms if female and normal ECG tracing unless the Investigator considers an ECG abnormality within described limits to be not clinically relevant
11. Stable or well controlled blood pressure per Investigator's judgement during the Screening Period. Specifically: Vital signs after 10 minutes sitting in a chair (feet on floor, back supported):
 - i. 95 mmHg < SBP < 160 mmHg,
 - ii. 45 mm Hg < DBP < 100 mm Hg,
 - iii. 40 bpm < HR < 100 bpm.
12. HbA1c < 9.0% at screening.
13. Patients with type 2 diabetes treated with metformin may be enrolled. However, patients with type 2 diabetes on any other therapy will be excluded.
14. Female subjects must have negative pregnancy test and must not be lactating. For females able to bear children, a hormonal (i.e., oral, implantable, or injectable) and single barrier method (i.e., sponge), or a double-barrier method of birth control (i.e., condom with spermicide) or abstinence must be used/practiced throughout the study and for 90 days following last dose of study medication; for effective form of birth control.
15. Females of non-childbearing potential, defined as surgically sterile (status post hysterectomy, bilateral oophorectomy, bilateral tubal ligation, bilateral salpingectomy, or bilateral tubal occlusion) or post-menopausal for at least 12 months (may be confirmed with a screening FSH level in the post-menopausal lab range), do not require contraception during the study.
16. Males with female partners of childbearing potential must agree to a double-barrier method if they become sexually active during the study and for 90 days following the last dose of the study medication. Male subjects must not donate sperm for 90 days following their participation in the study.

